## 9.6 Reporting and Exclusions

### 9.6.1 Evaluation of Toxicity

All patients will be evaluable for toxicity from the time of their first treatment with olaparib.

### 9.6.2 Evaluation of Response

All patients that finish at least 1 cycle of therapy will be considered evaluable for clinical response. Clinical efficacy (Cumulative Overall Response Rate, ORR) will be evaluated by MDS IWG 2006 criteria (Cheson *et al.*, 2006) and AML IWG 2003 criteria (Cheson *et al.*, 2003) after 6 cycles of treatment. Cumulative ORR will include CR, Cri, PR, marrow CR achieved at least at one point during these 6 cycles.

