## 9. STATISTICAL CONSIDERATIONS

### 9.1 Study Design/Endpoints

#### 9.1.1 Study Design

This is an open-label study of olaparib in advanced relapsed or refractory IDH1/2-mutant AML and MDS. The study will have 4 arms. Arm 1 will include patients with relapsed or refractory AML with no prior exposure to IDH inhibitors (inhibitor naïve). Arm 2 will be composed of patients with relapsed or refractory AML with prior exposure to IDH inhibitors. Arm 3 will include patients with relapsed or refractory MDS with no prior exposure to IDH inhibitors (inhibitor naïve). Arm 4 will be composed of patients relapsed or refractory MDS with prior exposure to IDH inhibitors.

The effect of PARP inhibitors is dependent on 2-HG levels, and 2-HG levels are high in both IDH inhibitor naïve patients, as well as in patients who relapse after IDH inhibitors. While 2-HG levels are suppressed in patients actively on IDH inhibitors (independent of response, which discourages concomitant administration), in patients who relapse after IDH inhibitors 2-HG levels are seen to increase despite continued IDH inhibitor therapy. This has been seen in numerous studies (*e.g.*, Intlekofer *et al.*, 2018). Therefore, we expect a rather similar efficacy of PARP inhibitors in both IDH inhibitor naïve and IDH inhibitor pre-treated patients.

For the null hypothesis, the CR rate is 30% in IDH inhibitor naïve AML patient, not for patients with previous IDHi exposure. For the MDS, population, the data for IDHi naïve patients are still limited and we will have a conservative estimate that the rate of response will be similar to AML. The null hypothesis for patients already treated with at least 1 line of therapy and an IDH inhibitor will be set at 5% given the absence of available options for either MDS or AML. Sample sizes and futility rules:

Cohort	H0	H1	Alpha 1 sided	beta	Sample size stage 1	Futility	Sample size total*	Efficacy
AML IDHi naïve	30	50	5	20	19	6 or less	39	17 or more
AML IDHi exposed	5	35	5	10	8	0	14	3 or more
MDS IDH I naïve	30	50	5	20	19	6 or less	39	17 or more
MDS IDHi	5	35	5	20	6	0	12	3 or more

exposed								
---------	--	--	--	--	--	--	--	--

The calculations are based on a Simon 2 Stage Minimax design.

\* without the drop-out rate of 15%

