The safety and efficacy will be evaluated by an independent data review committee at each critical step of the protocol. Given the patient population, we considered a potential drop-out rate of 15%. Expected monthly accrual is 3-4 patients per month, with a proposed total sample size of 94 patients, over 2 years.

Demographic information such as age and race will be tabulated. Descriptive statistics, including means, standard deviations, and ranges for continuous parameters, as well as percentages and frequencies for categorical parameters, will be presented. Adverse medical events will be tabulated. CTCAE Grade 3 and Grade 4 laboratory abnormalities will be listed.

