#### 9.1.2.1 Efficacy Evaluation

Clinical efficacy will be evaluated by MDS International Working Group (IWG) 2006 criteria (Cheson *et al.*, 2006) and AML IWG 2003 criteria (Cheson *et al.*, 2003) after 6 cycles of treatment. The primary endpoint will be cumulative composite CR (CR, CRi, CRh) and we will also record the cumulative ORR will include complete remission (CR), complete remission with incomplete blood count recovery (CRi), partial response (PR), and bone marrow complete remission (marrow CR/MLFS) achieved at least at one point during these 6 cycles.

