## 9.2 Sample Size/Accrual Rate

Expected monthly accrual is 3-4 patients per month, with a proposed total sample size of 94 patients, over 2 years.

Racial Categories	Ethnic Categories				Total
	Not Hispanic or Latino		Hispanic or Latino		
	Female	Male	Female	Male	
American Indian/ Alaska Native	1	1	1	1	4
Asian	2	2	0	0	4
Native Hawaiian or Other Pacific Islander	1	1	0	0	2
Black or African American	6	6	4	4	20
White	20	20	10	10	60
More Than One Race	2	0	2	0	4
Total	32	30	17	15	94

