#### 9.4.2 Evaluation of Objective Response Rate

The effectiveness of the drug in patients for each cohort will be independently assessed by composite CR rate (CR+CRi+CRh). Objective Response Rate (ORR) will be included as a secondary endpoint, calculated as a composite CR+MLFS+PR. The exact two-sided 95% confidence intervals for the ORR will be reported. For lifetime data analyses, e.g., overall and progression free survival, the study survival will be estimated using the Kaplan-Meier method with the 95% confidence intervals (CIs). The CI based on the Greenwoods variance will be reported. In addition, the possible risk factors will be compared for survival with log-rank test. For multivariate analysis, the proportional hazards Cox model will be applied to investigate potential prognostic factors, such as age and stage of disease on the survival data. The adjusted p-values of the odds ratios and the adjusted 95% confidence interval will be reported.

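### Section 9.6.2 limits response evaluation to patients who finish cycle 1, and nothing counts earlier leavers as non-responders, so the primary CR rate can be biased upward

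*Combined protocol and SAP*

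**What the plan says.** Section 9.6 (Reporting and Exclusions) sets two evaluable sets side by side. For toxicity, 9.6.1 says "All patients will be evaluable for toxicity from the time of their first treatment with olaparib". For response, 9.6.2 says "All patients that finish at least 1 cycle of therapy will be considered evaluable for clinical response", and then goes on to describe cumulative ORR over six cycles. A cycle is 28 days.

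The primary endpoint is defined elsewhere, without a population. Section 9.1.2.1 says "The primary endpoint will be cumulative composite CR (CR, CRi, CRh"), and 9.4.2 says "The effectiveness of the drug in patients for each cohort will be independently assessed by composite CR rate (CR+CRi+CRh"). The response table in 12.1 has categories for early deaths but does not say whether those patients enter the denominator.

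Section 9.1.1 sets the naive-arm null by saying "the CR rate is 30% in IDH inhibitor" naïve AML patients and carries the same figure to naive MDS. It does not say whether 30% describes all treated patients or those who complete a cycle. The arm totals are footnoted as "without the drop-out rate of 15" percent, and the text adds "we considered a potential drop-out rate of 15" percent. Neither statement says when drop-out happens, and no section gives a replacement rule.

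**The concern.** Each arm is a single-arm rate tested against a fixed null, so no control group shares the effect of an exclusion. Patients who leave in the first 28 days are mostly treatment failures. Section 3.2.6, for example, withdraws patients whose white count exceeds 50,000/mcl more than 14 days after starting, which can fall inside cycle 1. Dropping such patients removes non-responders from the denominator and almost nothing from the numerator, so the reported rate can only move up.

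Two things are at stake. The first is the reported composite CR rate and, if stage 1 waits for 19 evaluable patients, the strength of the futility look. The second is the error rate of the final test. The plan does not fix that rate in the two naive arms, because it depends on a replacement rule and a null population that are not stated.

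**Working it through.** **Inputs.** From the table in 9.1.1:
- Each naive arm: null 30%, target 50%, one-sided alpha 5%, power 80%; stop at 6 or fewer of 19; success at 17 or more of 39.
- AML exposed: null 5%; stop at 0 of 8; success at 3 or more of 14.
- MDS exposed: null 5%; stop at 0 of 6; success at 3 or more of 12.

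The fraction *d* lost in cycle 1 is assumed. Spreading the 15% drop-out evenly over six cycles gives 1 − 0.85^(1/6) = 2.7%, so 2.5% and 5% are used. No cycle-1 leaver is taken to be a responder.

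**Reproducing the plan.** The probability of success is the sum over x1 = 7 to 19 of P(X1 = x1) × P(X2 ≥ 17 − x1), with X1 ~ Bin(19, p) and X2 ~ Bin(20, p). At p = 0.30 this is 4.55%, and at p = 0.50 it is 80.4%. A minimax search returns the same 6/19 and 17/39. The exposed designs also reproduce, with alpha 2.86% (AML) and 1.79% (MDS).

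**Step 1: reported rate.** If the true rate in all treated patients is 30%, the rate among cycle-1 finishers is 0.30/(1 − d): 0.30/0.975 = 30.8% and 0.30/0.95 = 31.6%. In counts, 16 responders among 39 treated is 41.0%; with 2 leavers dropped, 16/37 = 43.2%.

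**Step 2: stage 1 counted on 19 evaluable patients.** P(X1 ≥ 7 of 19) at p = 0.30/(1 − d).

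**Step 3: final test, naive arms, leavers replaced to 39 evaluable, 30% describing all treated.** The two-stage formula at p = 0.30/(1 − d).

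| Cycle-1 loss (assumed) | Null rate among finishers | Null arm continues | Type I error, replaced |
|---|---|---|---|
| 0 (design) | 30.0% | 33.4% | 4.55% |
| 2.5% | 30.8% | 36.2% | 5.7% |
| 5% | 31.6% | 39.2% | 7.1% |

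Under these conditions the 5% line is crossed between 1% loss (4.97%) and 1.25% loss (5.08%).

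**Step 4: no replacement, stated counts kept.** With at most 39 treated and 17 responders required, success cannot be more likely than P(X ≥ 17) for X ~ Bin(39, 0.30), which is 4.998%. Simulation with stage 1 read at 19 evaluable patients gives about 4.7% at 2.5% and 5% loss. There is also no inflation if 30% describes finishers, because the evaluable rate under the null is then 30% itself.

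**Step 5: exposed arms, leavers replaced.** Using 0.05/(1 − d), AML exposed is 3.05% at 2.5% loss, 3.26% at 5% and 4.33% at 15%. MDS exposed is 1.92%, 2.05% and 2.75%.

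**Step 6: all-treated denominator.** If leavers count as non-responders and 30% describes all treated, type I error is 4.55% at any loss rate. Power is 80.4% if 50% describes all treated. If 50% describes finishers, the all-treated rate is 0.50 × (1 − d), and power is 75.9% at 2.5% loss and 71.0% at 5%.

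**The case against.** The strongest reply is that 9.6.2 goes on to speak of ORR, a secondary endpoint, and never says that early failures leave the primary denominator. That is fair: applying it to the composite CR is a reading. But its first sentence covers clinical response without limit, and if it does not apply, the primary test has no stated population at all. Wording is needed either way.

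Other provisions limit early exits. Section 3.1.16 asks for a life expectancy of at least 12–16 weeks. Section 12.1 expects two cycles in general before progression is judged, and naive patients stopped at the assessment after cycle 1 have already finished that cycle. These points stand and are a reason to keep the assumed loss small. The shift in the reported rate is also modest beside the sampling error: the exact 95% interval for 16/39 is roughly 26% to 58%. Review by an independent committee and sign-off before stage 2 are safeguards, but neither sets a denominator.

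A reader might infer more than the documents support:
- **That the trial's type I error exceeds 5%.** This needs 9.6.2 to govern the primary test, leavers to be replaced, and the 30% null to describe all treated patients; none of these is stated. The drop-out footnote points towards over-recruitment, but 9.2 says "with a proposed total sample size of 94 patients, over 2 years", which is below the arm sum of 39 + 14 + 39 + 12 = 104.
- **That the error is 16.5%.** That figure puts the whole 15% drop-out into cycle 1, for which there are no timing data.
- **That inflation is impossible without replacement.** This holds for the fixed counts. If the cut-offs were rescaled or re-derived for the evaluable number reached, which the plan does not provide for, the error would be 5.4–5.8% at 5% loss (4.7–4.9% at 2.5%).
- **That the exposed arms are safe at any loss.** AML exposed reaches 5.04% at 20%.

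**Conclusion.** The concern holds as a gap in the primary analysis population that should be fixed. The only response-evaluable set excludes patients who leave in cycle 1, and no section brings them back as non-responders. Read as the primary denominator, it overstates a true 30% by 0.8 to 1.6 percentage points at the assumed 2.5–5% loss. It also raises the chance that a null naive arm passes stage 1 by 2.8 to 5.8 points if that look is counted on 19 evaluable patients.

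The type I error of 5.7–7.1% is a conditional illustration for the two naive arms only. With the stated counts fixed and at most 39 treated, or with a null that describes finishers, the error stays at or below 5.0%. The exposed arms stay below 5% at losses up to 15%. Confidence is medium, because the loss rate is assumed and the link from 9.6.2 to the primary endpoint is inferred. The conflict between 94 and 104 exists independently of 9.6.2, is a separate point, and adds no weight here.

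**What to change.** In 9.6.2, define the primary efficacy population as all eligible patients who receive at least one dose of olaparib, and count anyone without a documented CR, CRi or CRh as a non-responder. Apply the existing stage-1 and final cut-offs (19/39, 8/14, 6/12) to that population, so that replacing cycle-1 leavers no longer affects the test. Keep cycle-1 finishers as a sensitivity analysis. In 9.1.1, state that H0 and H1 describe all treated patients.

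The cost is wording, plus a slightly lower reported rate. If the 50% target was meant for finishers, the stated 80% naive-arm power should be restated (about 76% at 2.5% loss, 71% at 5%) rather than enrolling more. Restoring 80% would otherwise take 42 or 50 patients per naive arm instead of 39.

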## 10. ADVERSE EVENTS: LIST AND REPORTING REQUIREMENTS

AE monitoring and reporting is a routine part of every clinical trial. The following list of AEs (Section 10.1) and the characteristics of an observed AE (Sections 10.2 and 10.3) will determine whether the event requires expedited reporting via the Medidata Rave **in addition** to routine reporting.

### 10.1 Comprehensive Adverse Events and Potential Risks List (CAEPR)

#### **Comprehensive Adverse Events and Potential Risks list (CAEPR) for Olaparib (AZD2281, NSC 747856)**

The Comprehensive Adverse Events and Potential Risks list (CAEPR) provides a single list of reported and/or potential adverse events (AE) associated with an agent using a uniform presentation of events by body system. In addition to the comprehensive list, a subset, the Specific Protocol Exceptions to Expedited Reporting (SPEER), appears in a separate column and is identified with bold and italicized text. This subset of AEs (SPEER) is a list of events that are protocol specific exceptions to expedited reporting to NCI (except as noted below). Refer to the 'CTEP, NCI Guidelines: Adverse Event Reporting Requirements' [http://ctep.cancer.gov/protocolDevelopment/electronic\\_applications/docs/aeguidelines.pdf](http://ctep.cancer.gov/protocolDevelopment/electronic_applications/docs/aeguidelines.pdf) for further clarification. *Frequency is provided based on 3449 patients.* Below is the CAEPR for Olaparib (AZD2281).

*NCI Protocol #:* 10264

*Version Date:* December 11, 2024

**NOTE:** Report AEs on the SPEER **ONLY IF** they exceed the grade noted in parentheses next to the AE in the SPEER. If this CAEPR is part of a combination protocol using multiple investigational agents and has an AE listed on different SPEERs, use the lower of the grades to determine if expedited reporting is required.

**Version 2.6, June 5, 2023**

Adverse Events with Possible Relationship to Olaparib (AZD2281) (CTCAE 5.0 Term) [n= 3449]			Specific Protocol Exceptions to Expedited Reporting (SPEER)
Likely (>20%)	Less Likely (<=20%)	Rare but Serious (<3%)	
BLOOD AND LYMPHATIC SYSTEM DISORDERS			
Anemia			Anemia (Gr 4)
		Febrile neutropenia	
GASTROINTESTINAL DISORDERS			
	Abdominal distension		
Abdominal pain			Abdominal pain (Gr 3)
	Constipation		Constipation (Gr 2)
Diarrhea			Diarrhea (Gr 3)
	Dyspepsia		Dyspepsia (Gr 2)
	Mucositis oral		
Nausea			Nausea (Gr 3)
Vomiting			Vomiting (Gr 3)
GENERAL DISORDERS AND ADMINISTRATION SITE CONDITIONS			
	Edema limbs		
Fatigue			Fatigue (Gr 3)
IMMUNE SYSTEM DISORDERS			
		Allergic reaction	
INFECTIONS AND INFESTATIONS			
	Upper respiratory infection		
	Urinary tract infection		
INVESTIGATIONS			
	Creatinine increased		
	Neutrophil count decreased		Neutrophil count decreased (Gr 4)
		Platelet count decreased	
	White blood cell decreased		
METABOLISM AND NUTRITION DISORDERS			
Anorexia			Anorexia (Gr 2)
MUSCULOSKELETAL AND CONNECTIVE TISSUE DISORDERS			
	Arthralgia		
	Back pain		Back pain (Gr 2)
	Muscle cramp		
	Myalgia		
	Pain in extremity		
NEOPLASMS BENIGN, MALIGNANT AND UNSPECIFIED (INCL CYSTS AND POLYPS)			
		Leukemia secondary to oncology chemotherapy	
		Myelodysplastic syndrome	
NERVOUS SYSTEM DISORDERS			
	Dizziness		Dizziness (Gr 2)
	Dysgeusia		Dysgeusia (Gr 2)
	Headache		Headache (Gr 2)
RESPIRATORY, THORACIC AND MEDIASTINAL DISORDERS			
	Cough		Cough (Gr 2)
	Dyspnea		Dyspnea (Gr 2)
		Pneumonitis	
SKIN AND SUBCUTANEOUS TISSUE DISORDERS			
	Rash maculo-papular		
		Skin and subcutaneous tissue disorders - Other (angioedema)	
		Skin and subcutaneous tissue disorders - Other (erythema)	

Adverse Events with Possible Relationship to Olaparib (AZD2281) (CTCAE 5.0 Term) [n= 3449]		Specific Protocol Exceptions to Expedited Reporting (SPEER)
	nodosum)	
VASCULAR DISORDERS		
	Vascular disorders - Other (venous thromboembolism)	

**NOTE: New Primary Malignancies other than MDS/AML**

New primary malignancies have been reported in <1% of patients. There were other contributing factors/potential alternative explanations for the development of the new primary malignancy in all cases, including documented *BRCA* mutation, treatment with radiotherapy and extensive previous chemotherapy including carboplatin, taxanes, anthracyclines and other alkylating and DNA damaging agents. Most are not attributed to olaparib.

This table will be updated as the toxicity profile of the agent is revised. Updates will be distributed to all Principal Investigators at the time of revision. The current version can be obtained by contacting [[contact]](mailto:[contact]). Your name, the name of the investigator, the protocol and the agent should be included in the e-mail.

**Adverse events reported on Olaparib (AZD2281) trials, but for which there is insufficient evidence to suggest that there was a reasonable possibility that Olaparib (AZD2281) caused the adverse event:**

**CARDIAC DISORDERS** - Atrial fibrillation; Cardiac disorders - Other (nodal rhythm); Chest pain - cardiac; Sinus bradycardia; Sinus tachycardia

**EAR AND LABYRINTH DISORDERS** - Tinnitus

**ENDOCRINE DISORDERS** - Hypothyroidism

**GASTROINTESTINAL DISORDERS** - Ascites; Colitis; Colonic obstruction; Dry mouth; Dysphagia; Enterocolitis; Esophageal stenosis; Flatulence; Gastroesophageal reflux disease; Gastrointestinal disorders - Other (gastrointestinal hemorrhage); Gastrointestinal disorders - Other (intestinal obstruction); Gastrointestinal disorders - Other (intestinal perforation); Ileus; Jejunal perforation; Obstruction gastric; Pancreatitis; Periodontal disease; Rectal hemorrhage; Small intestinal obstruction; Stomach pain

**GENERAL DISORDERS AND ADMINISTRATION SITE CONDITIONS** - Death NOS; Fever; Malaise; Non-cardiac chest pain

**IMMUNE SYSTEM DISORDERS** - Immune system disorders - Other (systemic inflammatory response syndrome)

**INJURY, POISONING AND PROCEDURAL COMPLICATIONS** - Dermatitis radiation; Fracture; Gastrointestinal anastomotic leak;

Injury, poisoning and procedural complications - Other (vena cava injury); Wound dehiscence

**INVESTIGATIONS** - Alanine aminotransferase increased; Aspartate aminotransferase increased; Blood bilirubin increased; GGT increased; Hemoglobin increased; Lipase increased; Lymphocyte count decreased; Serum amylase increased; Weight loss

**METABOLISM AND NUTRITION DISORDERS** - Dehydration; Hyperglycemia; Hypermagnesemia; Hypocalcemia; Hypokalemia; Hypomagnesemia; Hyponatremia

**MUSCULOSKELETAL AND CONNECTIVE TISSUE DISORDERS** - Avascular necrosis; Bone pain; Generalized muscle weakness; Muscle weakness lower limb; Muscle weakness upper limb; Neck pain; Rotator cuff injury; Soft tissue necrosis lower limb

**NEOPLASMS BENIGN, MALIGNANT AND UNSPECIFIED (INCL CYSTS AND POLYPS)** - Treatment related secondary malignancy; Tumor pain

**NERVOUS SYSTEM DISORDERS** - Amnesia; Ataxia; Cognitive disturbance; Concentration impairment; Encephalopathy; Intracranial hemorrhage; Peripheral sensory neuropathy; Reversible posterior leukoencephalopathy syndrome; Stroke; Syncope; Transient ischemic attacks

**PSYCHIATRIC DISORDERS** - Anxiety; Confusion; Delirium; Hallucinations; Insomnia

**RENAL AND URINARY DISORDERS** - Acute kidney injury; Renal and urinary disorders - Other (decreased glomerular filtration rate); Renal and urinary disorders - Other (hydronephrosis); Urinary tract obstruction

**REPRODUCTIVE SYSTEM AND BREAST DISORDERS** - Vaginal hemorrhage

**RESPIRATORY, THORACIC AND MEDIASTINAL DISORDERS** - Bronchopulmonary hemorrhage; Hypoxia; Oropharyngeal pain; Pleural effusion; Respiratory failure; Respiratory, thoracic and mediastinal disorders - Other (chronic obstructive pulmonary disease)

**SKIN AND SUBCUTANEOUS TISSUE DISORDERS** - Alopecia; Erythema multiforme; Pruritus

**VASCULAR DISORDERS** - Arterial thromboembolism; Flushing; Hot flashes; Hypertension; Hypotension; Peripheral ischemia; Thromboembolic event

**Note:** Olaparib (AZD2281) in combination with other agents could cause an exacerbation of any adverse event currently known to be caused by the other agent, or the combination may result in events never previously associated with either agent.5

## 10.2 Adverse Event Characteristics

- **CTCAE term (AE description) and grade:** The descriptions and grading scales found in the revised NCI Common Terminology Criteria for Adverse Events (CTCAE) version 5.0 will be utilized for AE reporting. All appropriate treatment areas should have access to a copy of the CTCAE version 5.0. A copy of the CTCAE version 5.0 can be downloaded from the CTEP website [http://ctep.cancer.gov/protocolDevelopment/electronic\\_applications/ctc.htm](http://ctep.cancer.gov/protocolDevelopment/electronic_applications/ctc.htm).
- **For expedited reporting purposes only:**
  - AEs for the agent that are ***bold and italicized*** in the CAEPR (*i.e.*, those listed in the SPEER column, Section 10.1) should be reported through Medidata Rave only if the grade is above the grade provided in the SPEER.
  - Other AEs for the protocol that do not require expedited reporting are outlined in Section 10.3.5.
- **Attribution of the AE:**
  - Definite – The AE *is clearly related* to the study treatment.
  - Probable – The AE *is likely related* to the study treatment.
  - Possible – The AE *may be related* to the study treatment.
  - Unlikely – The AE *is doubtfully related* to the study treatment.
  - Unrelated – The AE *is clearly NOT related* to the study treatment.

## 10.3 Expedited Adverse Event Reporting

### 10.3.1 Rave CTEP-AERS Integration

The Cancer Therapy Evaluation Program Adverse Event Reporting System (CTEP-AERS) integration enables evaluation of post-baseline AEs entered in Rave to determine whether they require expedited reporting, and facilitates entry in CTEP-AERS for those AEs requiring expedited reporting.

All AEs that occur after baseline are collected in Medidata Rave using the Adverse Event form, which is available for entry at each treatment or reporting period, and used to collect AEs that start during the period or persist from the previous reporting period. The Clinical Research Associate (CRA) will enter AEs that occur prior to the start of treatment on a baseline form that is not included in the Rave-CTEP-AERS integration. AEs that occur prior to enrollment must begin and end on the baseline Adverse Event form and should not be included on the standard Adverse Events form that is available at treatment unless there has been an increase in grade.

Prior to sending AEs through the rules evaluation process, site staff should verify the

following on the Adverse Event form in Rave:

- The reporting period (course/cycle) is correct, and
- AEs are recorded and complete (no missing fields) and the form is query-free (fields added to the form during study build do not need to be query-free for the integration call with CTEP-AERS to be a success).

The CRA reports AEs in Rave at the time the Investigator learns of the event. If the CRA modifies an AE, it must be re-submitted for rules evaluation.

Upon completion of AE entry in Medidata Rave, the CRA submits the AE for rules evaluation by completing the Expedited Reporting Evaluation form. Both NCI and protocol-specific reporting rules evaluate the AEs submitted for expedited reporting. A report is initiated in CTEP-AERS using information entered in Medidata Rave for AEs that meet reporting requirements. The CRA completes the report by accessing CTEP-AERS via a direct link on the Medidata Rave Expedited Reporting Evaluation form.

In the rare occurrence that Internet connectivity is lost, a 24-hour notification is to be made to CTEP by telephone at [contact]. Once Internet connectivity is restored, the 24-hour notification that was phoned in must be entered immediately into CTEP-AERS using the deep link from Medidata Rave.

Additional information about the CTEP-AERS integration is available on the CTSU website:

- Study specific documents: Protocols > Documents > Education and Promotion, and
- Expedited Safety Reporting Rules Evaluation user guide: Resources > CTSU Operations Information > User Guides.

NCI requirements for SAE reporting are available on the CTEP website:

- NCI Guidelines for Investigators: Adverse Event Reporting Requirements is available at [https://ctep.cancer.gov/protocolDevelopment/electronic\\_applications/docs/aeguidelines.pdf](https://ctep.cancer.gov/protocolDevelopment/electronic_applications/docs/aeguidelines.pdf).

